Once patients have consented to participation, subjects will be randomly assigned to either intervention or control group-both consisting of 22 patients. Consent will be obtained by referring physicians, or physical therapists at approved sites participating in the study [further details regarding consent procedure below]. At all physical therapy sites participating in the study, patient service representatives will be trained in the study recruitment, collecting patient enrollment paperwork and other clerical needs. Allocation will occur in blocks of 4 by opaque envelope. The envelopes will be generated by web based randomization software²¹ placed into opaque, sequentially numbered envelopes and delivered to participating physical therapy clinics prior to beginning recruitment. Two sites will contain 4 blocks of 4 envelopes, and one site will contain 3 blocks of 4, ensuring a total of 44 patients. If one site or another enrolls more patients, only a full block of 4 envelopes will be transferred to that site for further enrollment. The envelopes will be stored in the desk of the directing physical therapist at each location,

and only removed once a patient has been enrolled. Once patients consent to enroll in the study, they will receive the next envelope in sequence in the group of 4, and be allocated to either the intervention or control group. The envelope will contain a number which the treating physical therapist will then compare to the master allocation list, which will reveal which treatment group #1 or #2(intervention or control) the patient has been allocated; it will also contain the patient's assigned identification number (PID). The treating physical therapist will be responsible for communicating the subject's allocation and PID which will be contained in their envelope to the primary investigator, who will hold the confidential master list. Outcomes data will be collected in a separately in REDCap.

Blinding

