A combination of physical therapist ([name]), summer research assistant/fellow, and employed certified athletic trainer ([name]) will be assigned to follow through on data collection for the entirety of the follow up period. The research assistant and athletic trainer will have access to patient name, and contact information. They will be authorized to telephone the patient to remind them to fill out their follow up PRTEE and NPRS. If the subject has not filled out their online survey after the 3 standard emails, we will attempt to contact the subject by phone. Each patient may be contacted 3 times, with each phone call one week apart at each follow up time point (3, 6, 12 months). If they have not filled out their survey at that point, we will cease attempts. The subject may ask us not to contact them by phone at any time, and we will not follow up by phone for the remainder of the study.

The final survey will include questions on whether the patient has sought and received other treatment, such as: prescribed medication, surgical intervention, injection therapy, and return to physical therapy.

Serious adverse events will be reported to the IRRB at any time during the active treatment phase of physical therapy, and will be entered into REDCap. This data will also be directly communicated to primary investigators-[name]; [name]; [name], DPT by email and phone. Mild adverse events, such as muscle pain and bruising at the site of BFR cuff will be considered routine and communicated only if it limits ability to treat patient at follow up visits, or leads to alteration in care.

Data Points collected will include:

1. PRTEE and NPRS will be collected at the physical therapy visit at entry, and sixth or last therapy visit. It will be collected electronically by email, with phone call reminders if necessary at 3 months, 6 months, and 12 months from the date of enrollment.
2. Grip Strength (maximum and maximum pain free), and 1 repetition maximum will be collected at entry into study, and 6th / or last visit.

Statistical Analysis

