Descriptive statistics will be performed for demographic variables. Categorical variables will be reported as n (%) and will be analyzed by chi-square or Fisher's exact test as appropriate. Continuous variables will be reported as mean with standard deviation or median with interquartile range and analyzed by repeated measures ANOVA or non-parametric equivalent based on the normality of the data distribution. Analyses will be performed at each time point for the primary and secondary outcomes as the dependent variables and group assignment and time point (visit number) as factors. Paired t test or non-parametric equivalent may also be used for within group comparisons. Statistical analysis will be performed using IBM SPSS statistics version 24.0 and the level of significance set at p less than 0.05, two-sided.

Primary outcome analysis will be intention to treat at the 12 month time point. Per-protocol analysis will also be reported. Primary outcome will be reported as change from the PRTEE baseline score to the 12 month PRTEE score. The minimally clinically important difference (MCID) on the PRTEE is considered to be 10, and will be used as the benchmark for success of the treatment protocol. The primary outcome variable will be the comparison of the change in PRTEE in the intervention group, compared to the control group. Missing data will be dealt with after evaluation of the cause of the missingness; and potential strategies include complete case analysis, multiple imputation model, and inverse probability weighting.

RCT of standard PT vs. PT and BFR for the treatment of LE

Secondary outcomes will be comparison of the change in the NPRS between groups; change in 1 repetition maximum between groups; and change in grip strength between groups.

Multiple linear regression analysis will be performed to control for the effects of age, sex, length of condition, previous and current treatments, occupation on change in PRTEE from baseline to 3, 6 and 12 months.

Power Analysis

A two sample t test of normal mean difference assuming a group standard deviation of 10 PRTEE score points based on findings by Krogh, et. al. (2013)²⁴, a minimal clinically important difference of 10²⁵, a two-sided significance of 0.05, and a power of 80% resulted in a sample size of 17 per group. A dropout rate of 30% is expected, thus the plan is to recruit a total of 22 patients per group for a total of 44 subjects.

Ethical Considerations

Risks and Side Effects

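### The supportive PRTEE regression leaves out baseline PRTEE and does not limit its covariates to values recorded before randomisation

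*Combined protocol and SAP*

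**What the plan says.** The Statistical Analysis section makes the between-group comparison of PRTEE change at 12 months, by intention to treat, the primary analysis. After the secondary outcomes it adds a separate multiple linear regression to "control for the effects of age, sex, length of condition, previous and current treatments, occupation on change in PRTEE from baseline"; the outcome runs "on change in PRTEE from baseline to 3, 6 and 12 months". Six items are named: age, sex, length of condition, previous treatments, current treatments and occupation. The sentence names neither treatment group nor baseline PRTEE. It gives no coding for occupation or treatments, and no time at which current treatments are measured.

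Three other places bear on this:

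- **Data Collection, baseline list.** It includes occupation, symptom duration, current medications and previous epicondylitis treatments. It has no field called current treatments.
- **Data Collection, follow-up.** "The final survey will include questions on whether the patient has sought and received other treatment", covering prescribed medication, surgery, injections and return to physical therapy. The Secondary Outcomes section places this data collection at the 3, 6 and 12 month contacts and plans descriptive statistics only.
- **Outcomes assessment.** PRTEE is collected at the first visit, so a baseline score exists for the model.

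The Power Analysis section states: "A dropout rate of 30% is expected, thus the plan is to recruit a total of 22 patients per group for a total of 44".

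**The concern.** Three features of the regression are left open.

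1. A change score contains the baseline score, so baseline PRTEE is the one variable certain to be related to it in the absence of perfect tracking. Leaving it out gives up precision and leaves chance baseline imbalance uncorrected.
2. The timing of current treatments is undefined. A patient who is doing badly may seek an injection or more therapy. Conditioning on that care conditions on something the allocated treatment may have influenced.
3. With uncoded occupation and treatment items, the model could use many degrees of freedom in a small sample.

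At stake is an adjusted estimate on the primary endpoint's scale, printed beside the primary result. It could differ from that result because of choices made after the data are in.

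**Working it through.** **Inputs from the documents.** Difference 10; "assuming a group standard deviation of 10 PRTEE score points"; "a two-sided significance of 0.05, and a power of 80% resulted in a sample size of 17 per group"; 22 per arm; "A dropout rate of 30% is expected". The section does not say whether the SD is of the score or of the change. Here it is taken as the SD of the outcome analysed.

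**The plan's own figure.** The two-sample t calculation with difference 10, SD 10, two-sided 0.05 and 80% power gives 16.71, so 17 per group. This matches the plan.

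**Expected completers.** 44 × (1 − 0.30) = 30.8, about 31. The calculations below use 15 per arm (n = 30). The unadjusted SE is 10 × √(2/15) = 3.65, and exact-t power is 75.3%. The fall from 80% to 75% comes from the dropout allowance, not from the regression.

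**How many degrees of freedom.** Six items at one df each, plus group and intercept, make 8 parameters and leave 30 − 8 = 22 residual df. The baseline list gives at least five kinds of previous treatment. One indicator each (5), plus age, sex, duration and one current-treatment indicator (4), plus occupation in two groups (1), makes 10 df.

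**Cost in precision.** For k baseline covariates explaining a share R² of outcome variance, the SE is multiplied by about √[(1 − R²)(n − 3)/(n − k − 3)].

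- k = 6, R² = 0: √(27/21) = 1.13, SE 3.65 × 1.13 = 4.14
- k = 10, R² = 0: √(27/17) = 1.26, SE 3.65 × 1.26 = 4.60
- Break-even R² is k/27, so 22% for six df and 37% for ten.

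Simulation (8,000 trials per setting, 15 per arm, effect 10, SD 10; the 30% is an assumption):

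| Covariate df | Mean SE, R² = 0 | Power, R² = 0 | Power, R² = 30% |
|---|---|---|---|
| 0 | 3.6 | 75% | – |
| 6 | 4.1 | 63% | 79% |
| 10 | 4.5 | 54% | 70% |
| 15 | 5.3 | 42% | 55% |

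A second simulation gave 65% and 55% for six and ten uninformative df, so about 64% and 54–55% are fair summaries. In these n = 30 settings type I error ran from 4.4% to 5.4%.

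**Gain from baseline PRTEE.** Assume equal SD σ at baseline and follow-up, and correlation ρ between them. The change score has variance 2σ²(1 − ρ). After adjustment for baseline it is σ²(1 − ρ²). The ratio is (1 + ρ)/2. For an assumed ρ of 0.3 to 0.7 this is 0.65 to 0.85, so the SE is multiplied by √0.65 = 0.81 to √0.85 = 0.92, before a one-df cost of √(27/26) = 1.02.

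**If current treatments were taken at follow-up.** Every scenario input here is assumed: how strongly poor response drives further care, how many seek it, the correlation over time, and whether it works. Effects are shown as points of benefit.

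| Scenario | Total effect | Adjusted effect |
|---|---|---|
| Graded care-seeking, later care has no effect | 10.0 | 9.3 |
| Same, later care worth 5 points | 9.2 | 9.3 |
| Same, later care worth 10 points | 8.6 | 9.4 |
| Cut-off rule, worst 20–50% at 3 months, no effect, correlation 0.6, 3-month difference 10 | 10 | 6.1–7.4 |
| Same, 3-month difference 5 | 10 | 8.1–8.6 |

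The adjusted figure moves off the total effect in either direction, by amounts that the documents cannot fix.

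**The case against.** The strongest reply is that the plan does not say what a worried reader takes from it. The regression sentence gives no follow-up timing. Current treatments stand beside age, sex, duration and occupation, all of which are baseline fields, and the baseline list includes current medications. The Secondary Outcomes section assigns follow-up treatments a descriptive role only. On that reading there is no post-randomisation adjustment and no bias from it. This stands as far as it goes: a reader might infer that the plan adjusts for treatments at follow-up and so biases the effect toward no difference, and the documents support neither step. What remains is that the sentence does not exclude the follow-up fields, and no baseline field matches its term.

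The second reply is that covariates need not cost precision. This also stands in part. Six df that explain about 20–30% of the variance cost little or nothing, and the 10-df count is a plausible coding, not one the plan states. Ten df at 30% explained still fall below the unadjusted power (70% against 75%).

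The third reply is that the primary comparison is a separate analysis. That is correct. A reader might also take the loss of precision to mean more false positives; the simulated type I error rules that out.

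None of these replies explains the absence of baseline PRTEE.

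**Conclusion.** The point holds as a specification gap in a supportive analysis, and closing it is a free improvement. The firm part is that baseline PRTEE is collected but not named in a model for change in PRTEE. Including it would cut the variance to about 0.65–0.85 of the change-score analysis, if ρ is 0.3–0.7 and the SDs are equal.

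The other two parts are conditional. Use of follow-up treatments is possible under the wording but not stated; if it happened, the estimate would stop targeting the randomised effect, with no fixed size or direction. Loss of power from the covariate list, from about 75% to about 64% (six df) or 54% (ten df), requires uninformative covariates and, for ten, an expanded coding.

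Nothing here changes the primary intention-to-treat result or the type I error.

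**What to change.** Replace the regression sentence with one prespecified model:

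- Outcome: PRTEE change (or score) at each of 3, 6 and 12 months, with 12 months leading.
- Terms: treatment group, baseline PRTEE, and a short list of covariates recorded before randomisation, for example symptom duration, each with its coding stated.
- Keep treatments sought after therapy out of the model, and report them by arm under the descriptive analysis already planned in Secondary Outcomes.
- Label the regression as supportive of the primary intention-to-treat comparison.

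The cost is one paragraph of SAP text and no new data. The loss is an exploratory look at occupation and concurrent care; if that is wanted, it can be reported separately and labelled exploratory.

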This will be a randomized, controlled, open label trial. A total of 44 subjects will be recruited. Each group will be divided equally with 22 subjects having been diagnosed with lateral elbow pain. Subjects will be recruited from CCAG physicians located within the CCAG health system, as well as at physical therapy locations at Health and Wellness Centers in Bath, Green, and Stow. A team of physical and occupational therapists have been recruited including therapists and athletic trainers who are present at each office. At each site, 1 therapist will undergo a 2 hour standardized training session on delivery of treatment and data collection. Patients evaluated and found to have the appropriate criteria by either physicians or physical therapists will be given a research information sheet (see appendix) offering the opportunity to participate in a research study at the above mentioned locations. The patients interested will be consented by phone, or in person once they present to physical therapy office.

Timeline of Study

The goal is a 6-week treatment period at 1 PT visit per week. In ideal situation the visits occur in consecutive weeks, but will be considered per protocol with 6 visits over a 12 week period. Follow up will occur for 12 months after the initial therapy visit. We anticipate the total open period of time to last between 2-3 years for completion of 1 year follow up, 2019-2022.

- A patient can elect to drop from the study at any time.
- A patient's treatment will be considered completed if they cannot attend 6 visits within the 12 week time frame.
- A patient can be discharged from care prior to 6 weeks if all clinical goals set at the initial therapy assessment are met. If this occurs the outcomes measures expected at the 6th visit will be recorded at this visit and considered equivalent to the 6th visit outcomes.

Recruitment/Enrollment

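### Recruiting 22 per group does not leave the 17 evaluable patients needed for 80% power once the plan's own 30% dropout is applied

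*Combined protocol and SAP*

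**What the plan says.** The Power Analysis section sets out the calculation in two sentences. It uses "A two sample t test of normal mean difference", "assuming a group standard deviation of 10 PRTEE score points", a minimal clinically important difference of 10 points and "a two-sided significance of 0.05", and reports that "a power of 80% resulted in a sample size of 17 per group". It continues: "A dropout rate of 30% is expected, thus the plan is to recruit a total of 22 patients per group", for a total of 44. It gives no formula for the step from 17 to 22.

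The same numbers recur elsewhere. Brief Design Description says "A total of 44 subjects will be recruited" and "Each group will be divided equally with 22 subjects". Randomization/Allocation supplies two sites with 4 blocks of 4 envelopes and one site with 3 blocks, so 11 × 4 = 44 in all. Therapy Protocols gives 22 per arm, and Potential Limitations of Study refers to enrolling 44. No section describes replacing patients who drop out.

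**The concern.** An allowance for dropout should ensure that the number remaining after the losses equals the number the power calculation requires. That means dividing the required number by the fraction retained. Increasing the required number by the dropout percentage gives too few, because the losses are then taken from the larger, recruited number. Going from 17 to 22 for 30% dropout looks like the second method.

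The 80% power is then a property the design lacks under its own assumptions. The 10-point difference is also the plan's benchmark for success of the treatment, so the chance of detecting it matters when a null result is read. Such a result would be presented as coming from a trial with a one-in-five risk of missing a true 10-point difference, when the plan's inputs imply about one in four.

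**Working it through.** **Inputs** (all from Power Analysis unless noted): two-sample t test; difference 10; SD 10 in each group, so the standardised difference is 10 / 10 = 1.0; two-sided significance level 0.05; target power 80%; dropout 30%; 22 recruited per group; equal allocation (Brief Design Description).

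**Step 1: reproduce the 17.** With n evaluable patients per group, the test has 2n − 2 degrees of freedom and noncentrality 1.0 × √(n/2). Power comes from the noncentral t distribution.

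- n = 16: 78.1%
- n = 17: 80.7%

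So 17 is the smallest number per group that reaches 80%, and the plan's figure is right. The normal approximation gives 2 × (1.960 + 0.842)² = 15.7, so 16, which shows that the plan's 17 is the t-test figure.

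**Step 2: the dropout allowance.**

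- Required recruitment: 17 / (1 − 0.30) = 24.3, so 25 per group and 50 in total. Expected completers: 25 × 0.70 = 17.5.
- Planned recruitment: 22. Expected completers: 22 × 0.70 = 15.4, which is below 17.
- Likely origin of 22: 17 × 1.3 = 22.1.
- Dropout that 22 can absorb: 1 − 17/22 = 5/22 = 22.7%.

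**Step 3: power at the planned recruitment with 30% dropout** (t test on completers).

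| Evaluable patients | Power | Difference detectable with 80% power |
|---|---|---|
| 15 per group | 75.3% | 10.60 points |
| 15.4 per group (expected value) | 76.5% | 10.45 points |
| 15 and 16 (31 in total) | 76.7% | not computed |
| 17 per group (as planned) | 80.7% | just under 10 points |

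If each patient drops out independently with probability 0.30, power averaged over the binomial number of completers in each arm is 75.7%. The chance that a given arm of 22 keeps at least 17 is about 31%; for both arms it is 0.313² = 0.098, about 10%. With 25 recruited per group, the averaged power is 81.2%.

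**The case against.** The arithmetic is not in dispute. The case on the other side concerns its weight and its wording.

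- **The effect is small.** About 4 to 5 points of power are lost, and the detectable difference moves by about half a point. Bias, type I error and safety are unaffected. This stands, and it limits how much should be made of the point.
- **The assumed SD matters as much.** As an illustration with values not in the plan, an SD of 9.5 with 15.4 per group gives 80.6% power, while an SD of 10.5 with the full 17 per group gives 76.8%. This is true, but uncertainty in an input does not excuse a wrong step from the stated inputs.
- **The 1.3 multiplier is inferred.** It is, since no formula is given. The conclusion does not depend on it, because 22 less 30% is below 17 however 22 was reached.
- **The 80% is attached to 17, not in so many words to 22.** The plan derives 22 from 17 and the dropout rate with the word *thus*, so the reader is meant to carry the 80% over.
- **Dropouts may still contribute information.** The primary analysis is by intention to treat, PRTEE is also collected at the final therapy visit, 3 months and 6 months, and multiple imputation is one option. Some recovery is possible. However, complete case analysis is also listed, no method is fixed, and the power calculation credits no gain from imputation, weighting or covariates. The 75% to 76% should therefore be read as the complete-case power of the planning t test.
- **The normal approximation gives 79.2% at 15.4 per group.** That is close to 80%, but the plan names a t test and its 17 is the t-test result.

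**Conclusion.** The concern holds. Under the plan's own assumptions (difference 10, SD 10, two-sided t test at 0.05, 30% dropout, no replacement, dropouts contributing nothing to the 12-month comparison), 22 per group leaves about 15 evaluable patients per group and about 75% to 76% power, not 80%. The shortfall against the correct allowance is 3 patients per group, 6 in total. Power of 80% is reached only if no more than 5 of 22 patients per group (22.7%) are lost. The trial remains informative, but the sentence that justifies its size is wrong. All figures are conditional on the SD of 10, whose source cannot be checked from the documents.

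**What to change.** Keep 44 patients and correct the sentence in Power Analysis. Either of these would do:

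- *With 22 recruited per group and 30% dropout, about 15 patients per group will be evaluable, giving about 75% power to detect a 10-point difference (SD 10, two-sided 0.05).*
- *With 22 recruited per group, 80% power for a 10-point difference (SD 10) holds only if dropout is no more than 22%.*

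If the primary analysis will be adjusted for baseline PRTEE, the power should be stated for that analysis instead. The cost is one sentence and a slightly less favourable power figure, with no extra patients and no change in conduct. This suits the recruitment worry voiced under Potential Limitations of Study.

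The alternative is to keep the 80% claim and recruit 25 per group. As 50 is not a multiple of 4, full blocks would need 52 envelopes (26 per group). That adds 6 to 8 patients and requires matching changes in Brief Design Description, Randomization/Allocation, Therapy Protocols, Power Analysis and Potential Limitations of Study.
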